Trial Design:	
This is a Phase 2, randomised, open-label, parallel-group, multicentre trial in which the investigational product, MC2-01 cream, and calcipotriene/betamethasone ointment (comparator) is investigated in subjects with clinically diagnosed extensive psoriasis vulgaris.
 
After having provided informed consent, the subjects will undergo screening procedure. Subjects that fulfil the inclusion and exclusion criteria are randomly assigned in a 1:1 ratio to receive the MC2-01 cream or the comparator.
 
Subjects assigned to the MC2-01 cream will be treated once-daily for 8 weeks and the subjects assigned to the comparator will be treated once-daily for 4 weeks.
 
At Week 4, the pharmacokinetic (PK) profile of calcipotriene (CAL), betamethasone dipropionate (BDP) and their main metabolites MC1080 and betamethasone 17-propionate, respectively, will be assessed for both treatment groups. At Week 8, the PK profile of calcipotriene, betamethasone and their main metabolites will be assessed for the MC2-01 cream treatment group only.
 
The effect of use of MC2-01 cream on the hypothalamus-pituitary-adrenal (HPA) axis and calcium metabolism will be evaluated at week 4 and week 8.
 
The maximum trial duration for each subject will be approximately 12 or 16 weeks and includes a screening period of up to 4 weeks (if washout of medication is required), a treatment period of 4 or 8 weeks, and a follow-up period of up to 4 weeks (if required for follow-up of adverse events, calcium concentrations, and/or HPA axis suppression).

Sample Size:	
It is planned to enrol approximately 60 subjects with the aim to have 25 subjects included in the PK population after 4 weeks of treatment in each treatment arm.
 
The choice of sample size in this trial is not based on statistical considerations, but rather on regulatory considerations with respect to common practice in maximum use studies evaluating pharmacokinetic profiles and evidence of HPA safety

Trial Population:	Generally healthy males or non-pregnant females, at least 18 years of age, with a clinical diagnosis of plaque psoriasis (psoriasis vulgaris) of at least 6 months duration, with a Physician Global Assessment (PGA) of disease severity of at least moderate on the trunk, limbs and/or scalp and a treatment area between 20% and 30% of the BSA, excluding psoriatic lesions on the face, genitals, and intertriginous areas.

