#### 7.9.5 Pharmacokinetics

For all subjects, samples for PK testing will be collected through an untreated area of the skin, at the following time points:

- SV2/baseline visit: single time point
- Week 2 visit: single time point
- Week 4 visit: before application of IP at the visit and then at 0.5, 1, 2, 3, 5, and 7 hours after the end of the application

For subjects assigned to the MC2-01 cream, samples for PK testing will be collected at the following time points:

- Week 8 visit: before application of trial medication at the visit and then at 0.5, 1, 2, 3, 5, and 7 hours after the end of the application.

Subjects are to be instructed to apply their daily dose of trial medication in the morning on the day before the visit and not before the visit on the day of the visit. A reminder to the subject may be needed a few days before the scheduled visit.

The samples will be assayed for concentrations of the active ingredients (BDP and CAL) and for their major metabolites (betamethasone 17-propionate and MC180, respectively)

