### **8.3 Analysis Populations**

The analysis populations are defined as follows:

- **PK population:** all subjects in the Safety population who have received the planned application of treatment at the Week 4 or Week 8 visit, respectively, and have had at least one post-application blood draw for PK assessment at the corresponding visit.

- **Safety population:** all subjects who are randomized and have been dispensed the trial medication at Randomisation/Day 0, excluding subjects who return all of the trial medication unopened. The Safety population will be used for all safety analyses other than evaluation of the HPA-axis.
- **HPA population:** all subjects in the Safety population that are assigned to MC2-01 cream and who show normal HPA function at Baseline. Since the objective of the analysis is to estimate the risk to subjects with normal HPA function of HPA-axis suppression following treatment, subjects who meet the definition of HPA-axis suppression at Baseline will be excluded from the analysis. The HPA population will be used for the HPA axis suppression analysis.

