#### **8.7 Analysis of Pharmacokinetics**

All available concentration results will be summarised using appropriate descriptive statistics for active ingredients (BDP and CAL) and for their major metabolites. Median and individual concentration versus time curves will be plotted (linear and semi-log plots).

Plasma PK parameters ( $AUC_{0-t}$ ,  $AUC_{0-\infty}$ ,  $AUC_{0-7}$ ,  $C_{max}$ ,  $T_{max}$ , and  $T_{1/2}$ ) will be calculated at Week 4 and Week 8 (subjects randomised to MC2-01 cream only). The PK parameters  $AUC_{0-7}$  and  $C_{max}$  will be calculated using standard formulas inserting the lower limit of quantification for non-quantifiable levels of the analyte; therefore,  $AUC_{0-7}$  will be an upper limit in case at least one time point shows a non-quantifiable level of the analyte, and  $C_{max}$  will be an upper limit in case all time points show non-quantifiable levels of the analyte. For a given analyte, the PK parameters  $AUC_{0-t}$ ,  $AUC_{0-\infty}$ ,  $T_{max}$ , and  $T_{1/2}$  will be calculated if data allow. The PK parameters will be summarised using appropriate descriptive statistics including median, lower and upper quartiles, minimum and maximum.

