## 8. ANALYSIS POPULATIONS

Three analysis populations will be defined for analysis:

- Safety Population: will include all randomized subjects who have been dispensed the trial medication, excluding subjects who return all of the trial medication unopened. The Safety Population will be used for all safety analyses other than evaluation of the HPA-axis.
- HPA population: will include all subjects in the Safety population that are assigned to MC2-01 cream and who show normal HPA function at Baseline (defined as a 30-minute post-stimulation cortisol level  $\geq 18 \mu\text{g/dL}$ ). Since the objective of the analysis is to estimate the risk to subjects with normal HPA function of HPA-axis suppression following treatment, subjects who meet the definition of HPA-axis suppression at Baseline will be excluded from the analysis. The HPA population will be used for the HPA axis suppression analysis.
- Pharmacokinetic (PK) Population: will include all subjects in the Safety population who have received the planned application of treatment at the Week 4 or Week 8 visit, respectively, and have had at least one post-application blood draw for PK assessment at the corresponding visit. The PK Population will be used for the PK analysis.

---

All safety, HPA and PK analyses will be conducted according to the treatment actually received.

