### 10.9 Pharmacokinetics Analysis

All analyses of pharmacokinetics (PK) will be based on the PK population.

All available concentration results will be summarised using appropriate descriptive statistics (number of subjects, number of quantifiable concentrations, median, lower and upper quartiles, minimum, maximum) for active ingredients (BDP and CAL) and for their major metabolites. A listing for sample date/times as well as derived sampling time deviations will be provided. Median and individual concentration versus time curves will be plotted (linear and semi-log plots). Nominal sample collection times will be used in determining concentration descriptive statistics and plotting median concentration versus time profiles.

All analyte concentrations below the lower limit of quantification (BLOQ) will be reported as the lower limit of quantification (LLOQ) and will be treated as LLOQ in descriptive statistics and plasma concentration-time profiles.

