All Randomized Subjects  
[MC2-01 Cream][Active Comparator]

Subject Number	Date (Day)[1]	Study Drug Applied?	Reason if Medication not Applied
XX-XXX	DDMMYYYY (1)	Y	-
	DDMMYYYY (XX)	Y	-
	DDMMYYYY (XX)	N	XXXXXXX

[1] Study day is calculated relative to date of first application of study drug (Day 1).

Generated on XX/XX/XX:XXXX by XXXXX / Uses: XX

MC2 Therapeutics  
Protocol Number: MC2-01-C3

Page X of Y

Data Listing 16.2.5.4.2: Subject Food Diary  
All Randomized Subjects  
[MC2-01 Cream][Active Comparator]

Subject Number	Visit	Time Point	Date (Day)[1]	Number of Servings of Calcium-rich Foods	Reason Not Done
XX-XXX	Visit 1/Day 1	Day -3	DDMMYY YYYY (-3)	X	NA
		Day -2	DDMMYY YYYY (-2)	X	NA
		Day -1	DDMMYY YYYY (-1)	X	XXXXXXX
		Collection Day	DDMMYY YYYY (1)		

[1] Study day is calculated relative to date of first application of study drug (Day 1).

Generated on XX/XX/XX:XXXX by XXXXX / Uses: XX

Listing 16.2.6.1: Plasma Concentration Sample Date and Time and Plasma Concentrations  
 PK Population  
 [MC2-01 Cream] [Active Comparator]

Subject	Visit	Dosing Date and Time	PK Time Point	Sample Collection Date and Time (Day)	Elapsed Time (hours)	CAL (unit)	BDP (unit)	MC1080 (unit)	Betamethasone 17-propionate (unit)
XX-XXX	Baseline	--	--	DDMMYYYYTXX:XX (XX)	XX.X	XX.X	XX.X	XX.X	XX.X
	Visit 2/ Week 2	DDMMYYYYTXX:XX	Pre-dose	DDMMYYYYTXX:XX (XX)	XX.X	XX.X	XX.X	XX.X	XX.X
	Visit 3/ Week 4	DDMMYYYYTXX:XX	Pre-dose	DDMMYYYYTXX:XX (XX)	XX.X	XX.X	XX.X	XX.X	XX.X
			0.5 hour post-dose	DDMMYYYYTXX:XX (XX)	XX.X	XX.X	XX.X	XX.X	XX.X
			1 hour post-dose	DDMMYYYYTXX:XX (XX)	XX.X	XX.X	XX.X	XX.X	XX.X
			2 hours post-dose	DDMMYYYYTXX:XX (XX)	XX.X	XX.X	XX.X	XX.X	XX.X
			3 hours post-dose	DDMMYYYYTXX:XX (XX)	XX.X	XX.X	XX.X	XX.X	XX.X
			5 hours post-dose	DDMMYYYYTXX:XX (XX)	XX.X	XX.X	XX.X	XX.X	XX.X
			7 hours post-dose	DDMMYYYYTXX:XX (XX)	XX.X	XX.X	XX.X	XX.X	XX.X
			<etc.>						
	Visit 5/ Week 8	DDMMYYYYTXX:XX	Pre-dose	DDMMYYYYTXX:XX (XX)	XX.X	XX.X	XX.X	XX.X	XX.X
			0.5 hour post-dose	DDMMYYYYTXX:XX (XX)	XX.X	XX.X	XX.X	XX.X	XX.X
			<etc.>						

Listing 16.2.6.2.X: [CAL, BDP, MC1080, Betamethasone 17-propionate] Derived Pharmacokinetics Parameters  
PK Population  
[MC2-01 Cream] [Active Comparator]

Subject	Visit	C max (ng/mL)	T max (h)	AUC 0-7 (ng*h/mL)	AUC 0-t (ng*h/mL)	AUC 0-∞ (ng*h/mL)	T 1/2 (h)
XXX-XXX	Week 4	XXXX	XXXX	XX.XX	XXXXXX	XXXXXX	XXXX
	Week 8	XXXX	XXXX	XX.XX	XXXXXX	XXXXXX	XXXX

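### Week 2 (and Baseline) drug concentrations of subjects who never reach the Week 4 or Week 8 serial PK sampling appear in no planned table or listing

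*SAP*

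**What the plan says.** Protocol 7.9.5 schedules PK sampling for all subjects in both arms, including "Week 2 visit: single time point". The visit tables (Protocol Tables 7-2 and 7-3) show this as one pre-dose sample. Protocol 6.3 has subjects apply the product on the morning of the day before the visit and not before the visit on the day itself.

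On reporting, Protocol 8.7 says: "All available concentration results will be summarised using appropriate descriptive statistics for active ingredients (BDP and CAL) and for their major metabolites". It names no population at that point. SAP 10.9 repeats the promise, but directly after the sentence "All analyses of pharmacokinetics (PK) will be based on the PK population".

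SAP section 8 limits the PK population to Safety-population subjects meeting this condition: "have received the planned application of treatment at the Week 4 or Week 8 visit, respectively, and have had at least one post-application blood draw". Protocol 8.3 has the same rule: subjects must "have had at least one post-application blood draw for PK assessment at the corresponding visit".

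In the output list of SAP section 14, Tables 14.2.1.1 to 14.2.1.4 (concentrations by time point, one per analyte) are titled for the PK population. Their shell has Baseline and Week 2 rows. The shell for "Listing 16.2.6.1: Plasma Concentration Sample Date and Time and Plasma Concentrations" is also headed PK Population and also has a Week 2 row.

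On numbers, the protocol synopsis gives this plan: "enrol approximately 60 subjects with the aim to have 25 subjects included in the PK population after 4 weeks of treatment in each treatment arm".

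**The concern.** Whether a subject counts in the Week 2 row depends on something that happens later: being dosed and sampled at Week 4 or Week 8. The row therefore describes levels in those who went on to a serial profile, not levels in everyone sampled after two weeks of maximal use. For a subject who stops in between, the Week 2 sample is the only scheduled on-treatment concentration, because the Early Termination visit (Protocol 7.16) includes no PK draw. That value was measured, yet as the plan is written it is neither summarised nor listed.

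In a maximal-use trial, readers look at the highest observed concentrations and at how many samples were quantifiable. Both are columns of this table, and neither can go up when subjects are removed.

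**Working it through.** **Tracing the restriction**

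1. Entry to the PK population needs a post-application draw at Week 4 or Week 8 (SAP 8, Protocol 8.3). The Week 2 sample is taken before dosing at another visit, so it can never qualify a subject.
2. Outputs that contain Week 2 concentrations: Tables 14.2.1.1 to 14.2.1.4 and Listing 16.2.6.1, all headed PK Population. The figures cover only the Week 4 and Week 8 serial samples. Listings 16.2.6.2.X hold only Week 4 and Week 8 parameters and carry the same heading.
3. The general rule in SAP 9.1 lists variables used in the summaries. It does not clearly bring back values that the summaries leave out.
4. SAP section 11 does not record this as a change from the protocol.

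Two groups are not affected. A subject who stops after Week 4 dosing and sampling stays in the population. So does a cream subject with Week 8 serial PK only, if the definition is read as one pooled flag. The gap concerns subjects with neither profile.

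**How many subjects**

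Inputs from the synopsis: about 60 enrolled at 1:1, with 25 per arm in the PK population at Week 4.

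- Per arm: 60/2 = 30, and 30 − 25 = 5, so 5/30 = 16.7% may be outside.
- Overall: 60 − 50 = 10, and 10/60 = 16.7%.

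These figures only restate the planned numbers. The sample size is declared non-statistical and no dropout rate is given. Let f be the unstated share of those 10 who have a Week 2 sample. The values gained by the fix are 10f, out of 50 + 10f Week 2 values in all:

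| f | Values gained | Share of all Week 2 values |
|---|---|---|
| 0 | 0 | 0% |
| 0.25 | 2.5 | 2.5/52.5 = 4.8% |
| 0.5 | 5 | 5/55 = 9.1% |
| 0.75 | 7.5 | 7.5/57.5 = 13.0% |
| 1 | 10 | 10/60 = 16.7% |

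The replacement policy (Protocol 5.5) could take the number above 10.

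**What it could do to the reported statistics**

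The table reports N, number quantifiable, median, quartiles, minimum and maximum. If leaving is unrelated to exposure, the chance that the highest of 30 values is among k leavers is k/30: 3.3% for one, 6.7% for two, 16.7% for five.

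For the case where leaving is related to exposure, a simulation drew 30 log-normal values per arm (CV 50% and 100%, all quantified). It removed the k subjects with the highest score on a variable correlated 0.5 with log concentration. The correlation, its direction and the CVs are assumptions; the documents give none of them.

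| Leavers per arm (k) | Maximum lost, unrelated | Maximum lost, correlation 0.5 |
|---|---|---|
| 1 | about 3% of trials | about 18% |
| 2 | about 7% | about 30% |
| 5 (ceiling) | 16–17% | about 53% |

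With one or two leavers at correlation 0.5, the median falls by about 2–5% on average. SAP 10.9 sets values below the LLOQ to the LLOQ, so any such values would shrink these shifts.

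**The case against.** The strongest reply is that little depends on this sample. It is a single pre-dose draw about a day after the last application, so it is a trough. The primary endpoints are PK parameters at Week 4 and Week 8 (Protocol 4.2), and Week 2 concentration is not an endpoint. All of this stands. A reader might infer that the trial's maximal-exposure result or the between-arm ratio is biased. The documents do not support that: AUC0-7 and Cmax come from the serial profiles, and the fix would not change them.

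A second reply is that five leavers per arm is a ceiling. The gap between 60 and 50 also covers subjects with no Week 2 sample, such as those stopped because of Day 0 results. This stands too, and is why one or two leavers are shown alongside five.

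Third, a reader might assume that those who stop early absorb more. Nothing in the documents shows this. No laboratory or ACTH test is scheduled at Week 2, and the HPA-related stop follows the Week 4 test, at the visit where the serial samples are taken, so those subjects can still qualify. Leavers for local reactions or other reasons may absorb more or less. The one-sided argument holds for the maximum and the quantifiable count, not for the median or quartiles. Nor can the size be expressed as a shift in the geometric mean, because the SAP plans that statistic for the AUCs and Cmax, not for this table.

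Fourth, it is tempting to call this a flat contradiction. In the SAP, the promise of all available results follows the PK-population sentence and can be read as all results within that population. The protocol defines the same population. It is a tension in wording.

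Finally, Listing 16.2.3 shows who is outside the PK population and why. The exclusion is therefore visible, although the concentration is not.

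**Conclusion.** The gap is real but small. Followed as written, the plan drops measured Baseline and Week 2 pre-dose concentrations from every table and listing for any subject with neither a Week 4 nor a Week 8 serial profile. That follows from the population definition and the output headings, and rests on no simulation assumption.

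The number affected lies between 0 and about 5 of 30 per arm, or more with replacement. If nobody leaves between Week 2 and the serial visits, the Week 2 row does not change. The effect on the statistics is limited to descriptive troughs. The maximum and the quantifiable count can only stay the same or be understated, and the other summaries may move in either direction. The simulated percentages are illustrations under the stated assumptions, not predictions.

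This merits a low-priority correction. It casts no doubt on the Week 4 comparison.

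**What to change.** In SAP 10.9, keep the PK population for the serial profiles, the PK parameters and the ratio analysis. Add that Baseline and Week 2 concentrations are summarised for all Safety-population subjects with a sample at that visit, and label those rows of Table 14.2.1.X accordingly. Head Listing 16.2.6.1 Safety Population, with a flag for PK-population membership at Week 4 and at Week 8. The SAP already works this way for HPA: section 10.8.2.1 summarises suppression in the restricted HPA population but lists all test results for the Safety population.

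The cost is SAP wording and shell headings, with no new data. The one small drawback is that rows of the same table will have different denominators, which the N column already shows.

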#### 10.9.1 Analysis of Pharmacokinetic Parameters

Plasma PK parameters shown below ( $AUC_{0-t}$ ,  $AUC_{0-\infty}$ ,  $AUC_{0-7}$ ,  $C_{max}$ ,  $T_{max}$ , and  $T_{1/2}$ ) will be calculated at Week 4 in subjects randomized to comparator and MC2-01 groups and Week 8 in subjects randomized to MC2-01 cream only.

For a given analyte, the PK parameters  $AUC_{0-t}$ ,  $AUC_{0-\infty}$ ,  $T_{max}$ , and  $T_{1/2}$  will be calculated if data allow.  $AUC_{0-7}$  and  $C_{max}$  will be calculated using standard formulas inserting the lower limit of quantification (LLOQ) for non-quantifiable levels of the analyte; therefore,  $AUC_{0-7}$  will be an upper limit in case at least one time point shows a non-quantifiable level of the analyte, and  $C_{max}$  will be an upper limit in case all time points show non-quantifiable levels of the analyte.

$C_{max}$	Maximum plasma drug concentration. BLOQ Concentrations will be treated as LLOQ for this calculation
-----------	---

$T_{max}$	Time to maximum plasma drug concentration. If the maximum concentration value occurs at more than one time point, $T_{max}$ is defined as the first time point with this value
$AUC_{0-7}$	Area under the time-concentration curve from time zero to 7 hours, as calculated by the linear trapezoidal method. BLOQ Concentrations will be treated as LLoQ for this calculation
$AUC_{0-t}$	Area under the time-concentration curve from time zero to the last quantifiable concentration
$AUC_{0-\infty}$	Area under the time-concentration curve from time zero to infinity, calculated as $AUC_{0-t} + C_{tf}/\lambda z$ , where $C_{tf}$ is the last concentration $\geq$ LoQ. $AUC_{0-\infty}$ will be calculated only if $\lambda z$ can be calculated.
$T_{1/2}$	Elimination half-life, calculated as $\ln(2)/\lambda z$ . $T_{1/2}$ will not be calculated if $\lambda z$ cannot be determined
$\lambda z$	Elimination (terminal phase) rate constant, calculated as the slope of the terminal phase linear regression line of the log-scale concentration over the time points corresponding to the elimination phase of the concentration-time profiles. The elimination rate constant, $\lambda z$ , will not be calculated if the elimination phase of the log-linear concentration-time profile cannot be fit with an appropriate regression line. The time points corresponding to a subject's elimination phase will be identified by visually examining the log-scale concentration-time profile. A minimum of three points, not including $C_{max}$ , in which there is a relatively straight downward trend in concentration when plotted on a log scale, and the adjusted $R^2$ value for the fitted line must be at least 0.9 is required for the determination of $\lambda z$ . As an additional confirmation of the suitability of $\lambda z$ , the log-linear profile, which includes the regression line through the terminal points, will be checked via visual inspection, to determine whether the regression appropriately represents the terminal slope.

PK parameters will be listed and summarized using descriptive statistics (n, median, lower and upper quartiles, minimum and maximum) where appropriate. Geometric means and geometric CV will be calculated for  $AUC_{0-t}$ ,  $AUC_{0-\infty}$ ,  $AUC_{0-7}$ , and  $C_{max}$  as appropriate. An exception to this is  $T_{max}$  and  $T_{1/2}$  where only median, minimum, and maximum will be presented.

#### Assessment of systemic exposure (Week 4)

Assessment of relative systemic exposure in the two treatment arms will be performed for  $AUC_{0-7}$  and  $C_{max}$  at Week 4. If any of the post-dose time point shows a non quantifiable level of the analyte, the calculated PK parameters will be considered left censored. In particular,  $AUC_{0-7}$  will be considered censored if at least one post-dose concentration is below LLOQ.  $C_{max}$  will be considered censored if all post-dose values are below LLOQ. To account for the censored data, the SAS PROC LIFEREG procedure will be used on log-transformed PK parameters with treatment group as a fixed effect. Geometric mean ratio and associated 90% confidence interval (CI) (back-transformed from the estimates) will be presented.

## 10.10 Analysis of Other Endpoints

### 10.10.1 Physician Global Assessment of Psoriasis Severity (PGA)

PGA will be summarised using frequency counts and percentages for each treatment at Week 4 (all subjects) and at Week 8 (subjects assigned to MC2-01 cream). The proportion of subjects with treatment success, defined as a minimum 2-point decrease from Baseline in the PGA will also be summarized.

